1.5 Interim Analysis

There are no plans to conduct an interim analysis and no criteria by which the study would be terminated early based upon statistical determination.

2 ANALYSIS SETS

2.1 Safety Analysis Set

Safety analyses will be conducted using the safety analysis set on a treatment-emergent basis. As such, the safety analysis set will include all subjects/eyes exposed to any study lenses evaluated in this study. [REDACTED]

any adverse event (AE) or device deficiency occurring after Informed Consent and prior to the initial exposure to the study lenses (test or comparator) under evaluation in this clinical protocol will be listed as pre-treatment.

For treatment-emergent safety analyses, subjects/eyes will be categorized under the actual study lenses exposed in the corresponding lens sequence.

Adverse events occurring from the time of informed consent but prior to first exposure to study lenses will be summarized in subject listings.

2.2 Full Analysis Set

The full analysis set (FAS) is the set of all randomized subjects who are exposed to any study lenses evaluated in this study. [REDACTED]

2.3 Per Protocol Analysis Set

The per protocol (PP) analysis set is a subset of FAS and excludes all data/subjects that have met any of the critical deviation or evaluability criteria identified in the Deviation and Evaluability Plan (DEP).

3 SUBJECT CHARACTERISTICS AND STUDY CONDUCT SUMMARIES

The following tables will be presented:

- Subject Disposition by Lens Sequence
- Analysis Sets by Lens
- Analysis Sets by Lens Sequence
- Subject Accounting by Lens Sequence
- Demographics Characteristics by Lens Sequence
- Baseline Characteristics by Lens Sequence [lens brand, lens power: sphere, ADD]

Subject accounting and demographics characteristics tables will be summarized on the safety, full, and per protocol analysis datasets. Baseline characteristics will be summarized on the full and per protocol analysis datasets.

In addition, the following subject listings will be provided:

- Listing of Subjects Excluded from Protocol Defined Analysis Sets
- Listing of Lens Sequence Assignment by Investigator
- Listing of Subjects Discontinued from Study

4 EFFECTIVENESS ANALYSIS STRATEGY

This study defines 1 primary, [REDACTED] endpoint. Unless otherwise specified, effectiveness evaluations will use the FAS as the primary analysis set, [REDACTED]
[REDACTED]
[REDACTED]
[REDACTED]

Continuous variables will be summarized using the number of observations, mean, standard deviation, median, minimum, and maximum, as well as confidence intervals/limits as applicable. Categorical variables will be summarized with frequencies and percentages from each category.

[figure not shown]
All data obtained in evaluable subjects/eyes will be included in the analysis. No imputation for missing values will be carried out for the primary [REDACTED]

[figure not shown]
For all planned inferential analyses, alternative models/methods may be considered, for instance, if convergence cannot be achieved. Furthermore, if significant carryover effects are noted (confounded with sequence effect), results will be examined by period to ensure the overall conclusion is valid.

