12 ANALYSIS PLAN

Continuous variables will be summarized using the number of observations, mean, standard deviation, median, minimum, and maximum. Categorical variables will be summarized with frequencies and percentages from each category.

[figure not shown]
Any deviations to this analysis plan will be updated during the course of the study as part of a protocol amendment or will be detailed in the clinical study report.

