12.1 Subject Evaluability

Final subject evaluability must be determined prior to breaking the code for masked treatment (lens sequence) assignment and locking the database, based upon the Deviations and Evaluability Plan.

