12.4.1.2 Analysis Methods

A mixed effects repeated measures model will be utilized to test these hypotheses. The model will include terms for lens, visit, lens by visit interaction, period, sequence, and habitual lens stratum. Within-subject correlation due to the crossover design will also be accounted for in the model. Lens difference (MF minus AOHG MF) and the corresponding one-sided 95% upper confidence limit will be computed at Day 30. Noninferiority in distance VA will be declared if upper confidence limit is less than 0.05.

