**Clinical Performance Evaluation of Two Frequent
Replacement Silicone Hydrogel Multifocal Contact Lenses**

STUDY ID
CLN705-C001

[figure not shown]
STATISTICAL ANALYSIS PLAN

NCT05338333

Statistical Analysis Plan for CLN705-C001

**Title: Clinical Performance Evaluation of Two Frequent Replacement
Silicone Hydrogel Multifocal Contact Lenses**

Executive Summary:

Key Objectives:

The primary objective of this study is to demonstrate noninferiority (NI) in visual acuity (VA) at distance when wearing [REDACTED] Multifocal ([REDACTED] MF) contact lenses compared to AIR OPTIX® plus HydraGlyde® Multifocal (AOHG MF) contact lenses, after 30 days of wear.

[REDACTED]

[REDACTED]

[REDACTED]

Decision Criteria for Study Success:

Success of this study will be based on demonstration of noninferiority in VA with [REDACTED] MF contact lenses when compared to AOHG MF contact lenses, at Day 30, using a margin of 0.05 on the logMAR scale [REDACTED]

Table of Contents

Statistical Analysis Plan for CLN705-C001	1
List of Tables.....	4
List of Figures.....	4
1 STUDY OBJECTIVES AND DESIGN	5
1.1 Study Objectives.....	5
1.2 Study Description	5
1.3 Randomization.....	6
1.4 Masking	7
1.5 Interim Analysis.....	7
2 ANALYSIS SETS	7
2.1 Safety Analysis Set.....	7
2.2 Full Analysis Set.....	7
2.3 Per Protocol Analysis Set	8
3 SUBJECT CHARACTERISTICS AND STUDY CONDUCT SUMMARIES	8
4 EFFECTIVENESS ANALYSIS STRATEGY.....	8
[REDACTED]	
[REDACTED]	
[REDACTED]	
4.3.1 Primary Effectiveness Analysis	11
[REDACTED]	
[REDACTED]	
[REDACTED]	
[REDACTED]	
5 SAFETY ANALYSIS STRATEGY	14
5.1 Safety Endpoints.....	14
5.2 Safety Hypotheses	15
5.3 Statistical Methods for Safety Analyses	15
5.3.1 Adverse Events	15
5.3.2 Biomicroscopy Findings/Slit Lamp Examination	16
5.3.3 Device Deficiencies.....	16
[REDACTED]	

7	SAMPLE SIZE AND POWER CALCULATIONS	16
8	REFERENCES	17
10	APPENDIX	18

List of Tables

Table 1-1	Study Description Summary.....	5
Table 10-1	Schedule of Study Procedures and Assessments	18

List of Figures

[figure not shown]
Figure 1-1	Study Design.....	6
------------	-------------------	---

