4.3 Statistical Methods for Effectiveness Analyses

4.3.1 Primary Effectiveness Analysis

A mixed effects repeated measures model will be utilized to test these hypotheses. The model will include terms for lens, visit, lens by visit interaction, period, sequence, and habitual lens stratum. Within-subject correlation due to the crossover design will also be accounted for in

the model. Lens difference (████ MF minus AOHG MF) and the corresponding one-sided 95% upper confidence limit will be computed at Day 30. Noninferiority in distance VA will be declared if upper confidence limit is less than 0.05.

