7 SAMPLE SIZE AND POWER CALCULATIONS

Sample size required for [REDACTED] the primary effectiveness [REDACTED]
[REDACTED], at 90% power and one-sided $\alpha=0.05$, is summarized below:

Endpoint	SD (Paired Difference)	N/Sequence (NI margin = 0.05)
Distance VA	0.0845	13/Sequence
[REDACTED]	[REDACTED]	[REDACTED]
[REDACTED]	[REDACTED]	[REDACTED]nce

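### Does the SAP's open clause on alternative models leave the primary noninferiority test unfixed before unmasking?

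*SAP*

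**What the plan says.** SAP 4.3.1 and Protocol 12.4.1.2 specify a mixed effects repeated measures model for binocular distance visual acuity. On fixed effects: "The model will include terms for lens, visit, lens by visit interaction, period, sequence, and habitual lens stratum". On correlation: "Within-subject correlation due to the crossover design will also be accounted for in the model". The lens difference and its one-sided 95% upper limit are taken at Day 30, and noninferiority is declared if the limit is below 0.05. The SAP executive summary bases success on this comparison, "using a margin of 0.05 on the logMAR scale". SAP section 4 makes the full analysis set primary and rules out imputation for the primary endpoint.

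The sentence at issue is also in SAP section 4: "For all planned inferential analyses, alternative models/methods may be considered, for instance, if convergence cannot be achieved". The next sentence says that results will be looked at by period if carryover is noted, as a check on the overall conclusion.

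Protocol section 12 says deviations from the analysis plan are handled "as part of a protocol amendment or will be detailed in the clinical study report". Protocol 12.1 adds: "Final subject evaluability must be determined prior to breaking the code for masked treatment". No visible sentence sets the same deadline for the choice of model.

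**The concern.** The clause covers the primary test. Its trigger is open, it names no replacement and it sets no date. Reporting a deviation only in the study report could happen after the code is broken.

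The schedule of procedures gives four distance readings per subject: at dispense and at Day 30 with each lens. More than one covariance structure satisfies the sentence on within-subject correlation, and these structures can give different Day 30 standard errors. Study success rests on one upper confidence limit. If several models are admissible and one of them is valid at 5%, the chance that at least one passes cannot be below 5% and is usually above it. At stake would be the one-sided error rate, and the verdict for an observed difference close to the passing limit.

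**Working it through.** **Inputs.** From SAP section 7: paired-difference SD 0.0845, one-sided alpha 0.05, 90% power, margin 0.05, 13 per sequence for distance acuity. From SAP Table 1-1: 84 completers. The visible text gives no assumed true difference, so 0 is used for the sample size.

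**1. The plan's own figure.** Normal approximation: N = (0.0845 × (1.645 + 1.282) / 0.05)² = 24.5. With the noncentral t on N − 2 degrees of freedom, N = 24 gives 87.8% power and N = 26 gives 90.1%. So 26 in total, or 13 per sequence, is reproduced. The 84 completers come from near acuity (Protocol section 3), so the distance test has more than three times the subjects it needs.

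**2. Passing limit at 84.** SE = 0.0845 / √84 = 0.00922. Half-width = t(0.95, 82) × 0.00922 = 0.0153. The largest observed difference that passes is 0.05 − 0.0153 = 0.0347. Power is 99.99% at a true difference of 0, 99.6% at 0.01, 94.3% at 0.02 and 69.4% at 0.03.

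**3. Effect of the covariance choice on error.** The documents give no variance components, so the scenarios below are assumptions. Each uses 84 subjects with complete data, a true deficit of 0.05 and a Day 30 paired SD held at 0.0845, with 150,000 simulations per scenario. Entries are type I error in percent. The unstructured fit was approximated by feasible generalised least squares with a small-sample inflation.

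| Assumed structure | Random intercept | Day 30 only | Unstructured | Any of the three passes |
|---|---|---|---|---|
| No extra structure | 5.0 | 5.0 | 5.0 | 5.7 |
| Subject-by-period share 0.5 | 6.8 | 5.1 | 5.0 | 7.0 |
| Subject-by-period share 0.9 | 8.6 | 5.0 | 5.0 | 8.6 |
| Day 1 residual variance twice Day 30 | 2.3 | 5.0 | 5.0 | 5.4 |
| Subject-by-visit variance equal to residual | 1.7 | 5.1 | 5.1 | 5.4 |

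The share is the part of the non-subject variance that is common to both readings in a period. A random intercept pools all four readings, so its standard error is too small by a factor √(1 − share/3). For a share of 0.9 this is √0.7 = 0.837, which gives about 8.4% and agrees with the simulated 8.6%.

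**4. What free choice adds.** In the two scenarios with high error, the last column exceeds the random-intercept column by 7.0 − 6.8 = 0.2 and 8.6 − 8.6 = 0.0 points. Nearly all of that excess comes from one ill-fitting model. In the other three, passing on any model gives 5.4% to 5.7%, which is 0.4 to 0.7 points above nominal.

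A separate simulation used other assumptions: share 0 to 0.75, dispense-to-Day 30 residual SD ratio 0.7 to 1.3, 6,000 runs each. It gave 4.8% to 5.6% for Day 30 only, 3.3% to 9.2% for random intercept, and 5.2% to 9.2% for the better of the two. The maximum was again the random intercept's own error.

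**5. Effect on the verdict.** The random-intercept standard error ranges from 0.837 to 1.29 times the correct one. The passing limit then runs from 0.05 − 1.29 × 0.0153 = 0.0302 to 0.05 − 0.837 × 0.0153 = 0.0372. With SE 0.00922, the chance that the observed difference falls in this band is about 0.05% at a true difference of 0, 1.3% at 0.01 and 10% at 0.02. At equality, even the strictest limit is passed with probability Φ(0.0302 / 0.00922) = Φ(3.28), above 99.9%.

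**The case for a change.** The strongest case for a change is that high power does not protect the error rate at the margin. A few sentences naming a covariance structure, a degrees-of-freedom method and one fallback would remove the doubt at no cost in data. A random intercept does fit the sentence on within-subject correlation, and it can err in either direction (1.7% to 8.6%). It is also true that no visible text requires the model to be settled before unmasking. These points stand as a fair remark on drafting.

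They do not show a fault in the plan, for four reasons.

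- The plan does not commit to the fit that misbehaves, and nothing in the documents supports subject-by-period shares of 0.5 to 0.9.
- A replacement would be visible. The planned terms stand in both documents, Protocol section 4 requires an amendment for modifications, and Protocol section 12 requires deviations to be amended or reported. A reader could compare the two.
- Convergence with the real assignments is known only after unmasking. A rule can be fixed beforehand but the outcome cannot, so some provision for a fallback is reasonable.
- Parts of SAP section 4 and several entries after 4.3.1 are redacted. A covariance statement or fallback may be there.

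Error of 9.3% to 13.1% appears if a comparison in period 1 alone is also counted as a route to success. That is not a fair reading: SAP section 4 presents the by-period look as a check on the conclusion.

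**Conclusion.** No change is needed. In visible text only the covariance structure and the fallback model are open; the rest of the primary analysis is fixed. An analyst who follows the plan with an unstructured covariance, or who falls back on the Day 30 data alone, keeps the error at 5.0% to 5.1% in all five main scenarios. Outside the two scenarios where a random intercept is liberal, choosing freely among three models adds 0.4 to 0.7 points. The verdict is very unlikely to depend on the choice unless the true deficit is around 0.02 logMAR or more.

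This rests on the SAP's SD of 0.0845, on 84 completers with complete readings, and on variance components that are assumed. It does not establish performance with missing readings, and the unstructured fit was approximated. The clause is loosely worded, but it is a gap in detail and not an error in the analysis.

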Habitual lens information (brand, power, lens solution*)	X						
VA with habitual correction (OD, OS, Snellen distance)*	X				X	(X)	х
Keratometry (OD, OS)*	X						
Manifest refraction*	X	(X)	(X)	(X)	(X)	(X)	(X)
BCVA (OD, OS, Snellen distance and near with manifest refraction)*	X	(X)	(X)	(X)	(X)	(X)	(X)
Biomicroscopy	X	X	X		X	X	X

		LENS 1 (Period 1)		LENS 2 (Period 2)			
	Visit 1 Screening / Baseline / Lens Fit	Visit 2 Dispense Lens 1	Visit 3 Day 30 Follow-up Lens 1	Visit 3 Dispense Lens 2	Visit 4 Day 30 Follow-up Lens 2 / Exit	Unscheduled Visit	Early Exit
Procedure/ Assessment		Day 1 [3-5 days after Visit 1	Day 30 (- 2/+1) Days	Day 1 [same day as Lens 1 Day 30 Follow-up visit]	Day 30 (- 2/+1) Days	N/A	N/A
						Optional with Unplanned Lens Replacement only	
Inclusion/Exclusion criteria	X						
Randomize	X						
Study lens parameters optimization and fitting per randomization scheme (Test and Comparator)*	Х						

		LENS 1 (Period 1)		LENS 2 (Period 2)			
	Visit 1 Screening / Baseline / Lens Fit	Visit 2 Dispense Lens 1	Visit 3 Day 30 Follow-up Lens 1	Visit 3 Dispense Lens 2	Visit 4 Day 30 Follow-up Lens 2 / Exit	Unscheduled Visit	Early Exit
Procedure/ Assessment		Day 1 [3-5 days after Visit 1	Day 30 (- 2/+1) Days	Day 1 [same day as Lens 1 Day 30 Follow-up visit]	Day 30 (- 2/+1) Days	N/A	N/A
Study lens power to be dispensed	X						
Dispense study lenses per randomization scheme		X		X		(X)	
		•	•	•	•	-	•
LogMAR HC/HI VA at: • Distance (4 m or 3 m; OU)		X	X	X	X	(X)	X

		LENS 1 (Period 1)		LENS 2 (Period 2)			
	Visit 1 Screening / Baseline / Lens Fit	Visit 2 Dispense Lens 1	Visit 3 Day 30 Follow-up Lens 1	Visit 3 Dispense Lens 2	Visit 4 Day 30 Follow-up Lens 2 / Exit	Unscheduled Visit	Early Exit
Procedure/ Assessment		Day 1 [3-5 days after Visit 1	Day 30 (- 2/+1) Days	Day 1 [same day as Lens 1 Day 30 Follow-up visit]	Day 30 (- 2/+1) Days	N/A	N/A
							•
			•		•		

Page 25 of 67

		LENS 1 (Period 1)		LENS 2 (Period 2)			
	Visit 1 Screening / Baseline / Lens Fit	Visit 2 Dispense Lens 1	Visit 3 Day 30 Follow-up Lens 1	Visit 3 Dispense Lens 2	Visit 4 Day 30 Follow-up Lens 2 / Exit	Unscheduled Visit	Early Exit
Procedure/ Assessment		Day 1 [3-5 days after Visit 1	Day 30 (- 2/+1) Days	Day 1 [same day as Lens 1 Day 30 Follow-up visit]	Day 30 (- 2/+1) Days	N/A	N/A
Adverse Events	X	X	X	X	X	X	X
Device deficiencies	X	X	X	X	X	X	X
Exit Form	(X)	(X)	(X)	(X)	X		X

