1.2 Study Description

Key components of the study are summarized in Table 1-1.

[figure not shown]
Table 1-1 **Study Description Summary**

Study Design	Prospective, randomized, [REDACTED] bilateral, crossover, double-masked
Study Population	The subject population consists of volunteer subjects aged \geq 40 years, who are habitual daily disposable and biweekly/monthly replacement soft multifocal contact lens wearers for at least past 3 months and wear their habitual lenses at least 5 days per week and at least 8 hours per day. Target to complete: 84 Planned to enroll: ~96
Number of Sites	~8 US
Test Product	[REDACTED] Multifocal contact lenses ([REDACTED] MF; lehfilcon A; LID210464)
Comparator Product	AIR OPTIX [®] plus HydraGlyde [®] Multifocal contact lenses (AOHG MF; lotrafilcon B)

Planned Duration of Exposure	~60 days total duration (test and comparator): Test Product: 30 (-2/+1) days Comparator Product: 30 (-2/+1) days
Visits	Visit 1: Screening/Baseline/Lens Fit Visit 2: Dispense Lens 1 [3-5 days after Visit 1] Visit 3: Day 30 Follow-up Lens 1/Dispense Lens 2 [Day 30 (-2/+1)] Visit 4: Day 30 Follow-up Lens 2/Exit [Day 30 (-2/+1)] [REDACTED] [REDACTED]

A study design schematic is depicted in Figure 1-1.

Figure 1-1 Study Design

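### Does examining results by period after a significant sequence effect undermine the noninferiority conclusion?

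*SAP*

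**What the plan says.** The primary model in SAP 4.3.1 is a repeated-measures mixed model: "The model will include terms for lens, visit, lens by visit interaction, period, sequence, and habitual lens stratum". It has no separate carryover term, so on the visible text the sequence term is the only carryover signal. Section 4 of the SAP sets the response: "if significant carryover effects are noted (confounded with sequence effect), results will be examined by period to ensure the overall conclusion is valid". The visible text gives no significance level for this trigger, does not say what the examination consists of, and attaches no consequence to it. Parts of section 4 are redacted and may cover these points.

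The decision rule is stated separately, in Protocol 12.4.1.2 and again in SAP 4.3.1: "Noninferiority in distance VA will be declared if upper confidence limit is less than 0.05". It carries no condition about the sequence term or the separate periods.

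Three other features matter. Distance logMAR acuity is read at dispensing and at Day 30 in each period (Protocol Table 3-1). Lens 2 is dispensed at the Lens 1 Day 30 visit, so there is no washout between lenses. SAP section 4 also states: "No imputation for missing values will be carried out for the primary" endpoint, so subjects with Period 1 data only can contribute to the model.

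**The concern.** A validity check should behave differently when the conclusion is sound and when it is not. Here the check is run only after a significant sequence effect, and that effect is nearly the same quantity as the disagreement between periods. The periods will therefore tend to disagree whenever the check is run, and disagreement alone cannot say whether carryover or a chance difference between the two sequence groups is the cause. The SAP itself notes that the two are confounded.

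Two misreadings would be at stake. A reader could doubt a sound noninferiority result because of chance imbalance between groups. Or a reader could take agreement between two imprecise period estimates as confirmation. With neither a trigger level nor a consequence visible, the weight given to the table could be settled after unmasking.

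**Working it through.** **Inputs from the documents.** Paired-difference SD 0.0845, margin 0.05, one-sided alpha 0.05 and 90% power (SAP section 7); 84 completers, so 42 per sequence (SAP 1.2: "Target to complete: 84 Planned to enroll: ~96").

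**Assumptions, not in the documents.** Between-period correlation rho of 0.3, 0.5 or 0.7; correlation 0.5 between dispensing and Day 30 residuals within a period; a 0.05 level for the sequence test unless stated otherwise. Habitual lens stratum is not simulated. Triplets below follow the order of rho.

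**1. The plan's own figure.** Total N = (0.0845 × (1.645 + 1.282) / 0.05)² = 24.5, so 25 subjects and 13 per sequence, as SAP section 7 states.

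**2. The identity.** Let Yij be the Day 30 mean for sequence i in period j, with sequence 1 starting on the test lens. The test-minus-comparator differences are d1 = Y11 − Y21 and d2 = Y22 − Y12. Then d1 − d2 = (Y11 + Y12) − (Y21 + Y22), which is the sequence contrast. The crossover estimate is (d1 + d2)/2. The planned sequence term pools dispensing and Day 30 readings, so the identity is approximate there; the simulated correlation between that term and the Day 30 gap is 0.93/0.96/0.98.

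**3. Precision.**
- Crossover: SE = 0.0845/√84 = 0.0092.
- One measurement: SD = 0.0845/√(2(1 − rho)) = 0.0714/0.0845/0.1091.
- One period: SE = SD × √(2/42) = 0.016/0.018/0.024.
- Gap d1 − d2: SE = 0.0251/0.0319/0.0439. On Day 30 data alone, the smallest gap significant at two-sided 0.05 is about 0.050/0.064/0.087, at or above the whole margin.

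**4. Equal lenses, no carryover.** The crossover succeeds in over 99.9% of trials. Among chance triggers, at least one period's upper limit misses 0.05 in about 58%/90%/99.8%. At a 0.10 trigger it is 48%/82%/99.4%. By point estimates, the worse period reaches 0.05 in only 3%/11%/47% of triggers at the 0.05 level.

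**5. Matched comparison.**
- Case (i), noninferiority correct: true difference 0.025, no carryover, so d1 and d2 both average 0.025.
- Case (ii), noninferiority wrong: true difference 0.05, with carryover of 0.05 in Period 2, so d1 averages 0.05, d2 averages 0 and the crossover estimate averages 0.025.

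In both, crossover success is about Φ((0.05 − 0.025)/0.0092 − 1.66) = Φ(1.05) = 85%. Among triggers with crossover success:

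| Finding | Case (i) | Case (ii) |
|---|---|---|
| Either period's upper limit misses 0.05 | 99.0%/99.98%/100% | 99.6%/99.99%/100% |
| Period 1 upper limit misses 0.05 | 50%/50%/48% | 99.6%/99.9%/99.4% |
| Period 1 estimate is 0.05 or more | 25%/39%/47% | 69%/87%/98% |

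The first row shows no separation, because it merges a worse Period 1 with a worse Period 2. The other rows separate the cases. Period 1 cannot contain carryover from the other study lens, and a worse Period 1 is the pattern in which the crossover estimate may be too favourable.

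**6. If the look were a veto.** Suppose success is withdrawn when the trigger fires and either period misses 0.05.
- With equal lenses, power is about 1 − 0.05 × (0.58/0.90/0.998) = 97.1%/95.5%/95.0%. At a 0.10 trigger it is 95.2%/91.9%/90.1%.
- Type I error at a true difference of 0.05 without carryover is 4.4% to 4.8%, so it is not inflated.
- In case (ii), false success falls from about 85% to about 38%/54%/67%. The trigger limits this protection, since it fires in only 56%/36%/21% of such trials.

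**The case for a change.** The strongest case for a change is that the SAP sets up a data-triggered check on validity and then leaves its level, content and consequence unstated, at least in the visible text. The identity in step 2 needs no assumption about rho. One sentence making the by-period table descriptive would fix its status in advance at no cost in data. Carryover is also better argued from the design, since the endpoint is read after 30 days on each lens.

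Part of this stands. Disagreement between periods after a trigger does not by itself separate carryover from chance, and a worse Period 1 arises by chance in about half of triggers. Period 1 alone is also imprecise.

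Three things limit the objection. First, the missing details would belong in a section that is partly redacted, so their absence cannot be counted as a defect. Second, the claim that the look is uninformative depends on asking whether either period fails. The SAP states no such rule, and reading Period 1 on its own gives a clearly different answer in the two cases. Third, a sentence denying the look any role would either restate the unconditional rule or give up the plan's only visible response to suspected carryover.

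**Conclusion.** No change is needed. The algebra is right: a significant sequence effect and a Day 30 disagreement between periods are largely one contrast. The analyst should read the by-period results with that in mind and pay attention to which period is worse.

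On the visible text the noninferiority decision rests on the crossover upper limit alone, so rewording the by-period sentence would alter no result. If someone did apply the look as a veto, removing it would be a trade-off: about 3 to 5 points of power regained at a 0.05 trigger, or 5 to 10 at 0.10, against lost protection when carryover is present. There would be no type I error inflation to cure.

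The percentages depend on the assumed rho, residual correlation and trigger level, and case (ii) assumes carryover as large as the whole margin after 30 days on the second lens. The identity and the unconditional decision rule depend on none of these. Saying in the report that the by-period table is descriptive, and that Period 1 is free of carryover from the other study lens, would be a courtesy to readers.
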